## **6.4 Reporting urgent safety measures**

If any urgent safety measures are taken the CI/Sponsor shall immediately and in any event no later than 3 days from the date the measures are taken, give written notice to the relevant REC of the measures taken and the circumstances giving rise to those measures.

## **7 DATA MANAGEMENT**

### **7.1 Data collection and management**

The Case Report Form (CRF) will comprise of a set of forms capturing details of eligibility, baseline characteristics, treatment, and outcome details. This trial will use an electronic data capture (EDC) system which will be used for completion of the CRF. Access to the EDC system will be granted to approved site personnel via the Trial Office. If the use of a paper CRF is required, then original forms should be sent to the co-ordinating team at WCTU and copies retained on site. CRFs are expected to be completed within 4 weeks of their due date. Data reported on each form should be consistent with the source data or the discrepancies should be explained. If information is not known, this must be clearly indicated on the form. Missing

and ambiguous data will be queried in line with the WCTU data management plan, which will outline the requirements for CRF completion and return.

## **7.2 Source Data**

Source documents are where data is first recorded, and from which participants' CRF data is obtained. These include, but are not limited to, hospital records (from which medical history and previous and concomitant medication may be summarised into the CRF), clinical and office charts, laboratory and pharmacy records, diaries, microfiches, radiographs, and correspondence.

CRF entries will be considered source data if the CRF is the site of the original recording (e.g., there is no other written or electronic record of data). All documents will be stored safely in confidential conditions. On all trial-specific documents, other than the signed consent, the participant will be referred to by the trial participant number, not by name. Investigators should keep records of all participating patients, all original signed informed consent forms and copies of any paper CRFs. It is necessary for investigators to provide access to source document for monitoring and audit purposes to WCTU, Sponsor, any monitoring or regulatory authorities as deemed necessary.

## **7.3 Data Handling and Record Keeping**

The database will be developed and managed by the Programming Team at WCTU and all specifications (i.e. database variables, validation checks, screens) will be agreed between the programmer and appropriate trial staff. The database will meet industry standard security criteria and only be accessible to authorised personnel. Within the database, participants will be identified by the trial participant number only.

All essential documentation and trial records will be stored by WCTU in conformance with the applicable regulatory requirements and access to stored information will be restricted to authorised personnel.

Interview data and recordings of appointments will be recorded using secure encrypted audio devices or using Microsoft Teams. Recordings will be downloaded as soon as possible to encrypted university laptops and subsequently to the secure study area on the university servers under the participants unique study identifier. Once downloaded, the original audio recording will be deleted from its source. Any data that are transferred out of the secure environment (for example audio files of interviews for transcription) will adhere to University of Warwick SOPs. Any transcription service used will be subjected to the University of Warwick's approved supplier review processes. Audio files will be fully pseudonymised at the point of transcription, with any participant identifiers removed. Pseudonymised transcriptions will then be saved to a secure encrypted folder, under the unique patient identifier. The study team will maintain a separate confidential and secure list of patient identifiable information (name, identification number and contact details) for the purposes

of the process evaluation research (e.g., organising interviews), co-ordinating appointments, audit / quality assurance. This will be securely held on the University of Warwick servers.

Personal data entered onto myfood24 (such as name and email address) for the purposes of sending the food diaries to the participants will be held externally, securely stored on the Amazon Web Services Europe 'cloud' servers located in Dublin, with back-up servers in London. It has physical and environmental security controls plus the network connection is encrypted and protected by a firewall. myfood24 has multiple data security accreditations including ISO27001, Cyber essentials plus and NHS Data Security and Protection Toolkit (DSPT) guidelines. Where participants are unwell or unable to input food diaries directly on to myfood24, paper versions will be made available. Pseudonymised paper copies will be transferred to the PROPEL trial office for data entry.

#### **7.4 Access to data**

Direct access will be granted to authorised representatives from the Sponsor, the WCTU monitoring team, host institution and the regulatory authorities to permit study-related monitoring, audits and inspections. The CI, Process Evaluation Lead and the WCTU administrator (or delegate) will have access to the final study data set for the process evaluation.

#### **7.5 Data access and quality assurance**

The study will be conducted in accordance with the General Data Protection Regulation (GDPR). The investigator must ensure that participant's anonymity is maintained throughout the study and following completion of the study. To preserve anonymity, participants will be identified on all study specific documents (except for the informed consent form and enrolment log) by only the participants study specific identifier (and initials where deemed necessary to maintain patient safety). This identifier will be recorded on documents and the database. The Investigator Site File will hold an enrolment log detailing the study specific identifier alongside the names of all participants enrolled in the study.

All documents will be stored securely with access restricted to study staff and authorised personnel.

To support the remote intervention delivery, the participant will be asked for their consent to provide their name and contact details (email address and telephone number) and for this to be shared with the central PROPEL team of specialists. This is required for the organisation of remote appointments and to support participant safety.

In addition, patients will be asked if they would be willing to be contacted to be interviewed as part of the process evaluation. A sample of patients who agree to be contacted to be interviewed will be asked to provide their name and address to enable a qualitative researcher to contact the patient. Interviews will be audio recorded and will be stored electronically and identified by trial number only.

Personal data, including name, contact details will be stored securely on the database and security roles would be applied to ensure only those people who require access to participant identifying data are granted access. Participants should be assured that their confidentiality will be respected at all times.

UHCW and the University of Warwick will act as joint data controllers for this study.

## **7.6 Archiving**

At the end of the study, following completion of the end of study report, UHCW and WCTU will securely archive all centrally held study related documentation for a minimum of 10 years. At the end of the defined archive period arrangements for confidential destruction will be made. It is the responsibility of each PI to ensure that data and all essential documents relating to the study are retained securely for a minimum of 10 years after the end of study, and in accordance with national legislation. WCTU will notify sites when study documentation held at sites may be archived, and then destroyed. All archived documents must continue to be available for inspection by appropriate authorities upon request. Trial documentation and data will be archived for at least ten years after completion of the trial.

## **8 STATISTICAL ANALYSIS**

### **8.1 Power and sample size**

A sample size of 300 patients in each arm (600 in total) will allow the detection of a standardised difference of 0.3 in the continuous fatigue subscale scores of the Functional Assessment of Chronic Illness Therapy fatigue scale (FACIT-F) for the comparison of PPCP and BPUC with 90% power, 5% two-sided significance and allowing for 20% dropouts. The sample size calculation was determined using the POWER procedure within the SAS statistical software for a two-sample t-test.

A standardised difference of 0.3 equates to a minimally important clinical difference (MCID) of 4 points with a standard deviation of 13 using the FACIT-F fatigue subscale (which is a 13 item scale with scores 0-52) [11]. This MCID was based on the previous research from other studies [1] and considered acceptable after discussions with fatigue experts, AML clinicians and our PPI representatives.

### **8.2 Statistical analysis of efficacy and harms**

#### **8.2.1 Statistics and data analysis**

A detailed statistical analysis plan (SAP) will be produced to provide full details of all statistical aspects of the study. All analyses and reporting of outcomes will be in accordance with CONSORT [52], with primary analysis conducted according to randomised allocation and intention to treat principles.

The primary analysis will be a pragmatic comparison of the PPCP versus BPUC on an intention to treat basis to preserve randomisation and avoid bias. Sensitivity analyses will investigate the effect of the personalised nature of the intervention on any treatment effects and the effect of compliance using a complier averaged causal effect (CACE) analysis.

All measures will be scored according to the appropriate scoring manual and summary measures obtained for each timepoint. A longitudinal mixed effects regression model will be used to estimate the effect of the intervention compared to standard care on fatigue adjusted for patient-level factors including age, performance status and treatment received. The specialist that delivers the interventions will also be considered for inclusion as a random effect in the model although we expect the variation to be negligible due to the large number of specialists across sites. The effect of red cell transfusion use on the outcome will be considered as time-dependent effect, considering haemoglobin levels and timing of transfusions, as anaemia is a universal complication in AML. The individual need, compliance and intensity of the intervention including the number and amount of each component delivered will be investigated and their need for inclusion in the mixed effects regression model evaluated. Exploratory analyses will investigate intervention and covariate interactions to identify any subgroups where the intervention may work differently to the whole population.

Similar longitudinal analyses will be performed for the secondary QoL outcomes. Time to event outcomes, including the overall survival and relapse-free survival, will be assessed using Kaplan-Meier curves and compared across trial arms using Cox proportional hazards models, adjusted for the stratification factors. The impact of fatigue on these time to event outcomes will also be evaluated using Cox models. Completion of consolidation treatment plan including chemotherapy and HSCT, readmissions to hospital, ICU admission, number of transfusions, complications of HSCT will be compared across trial arms using logistic regression models. Adverse events and serious adverse events will be tabulated and compared if appropriate.

A sensitivity analysis will be considered to determine the degree to which the conclusions may change with different missing data assumptions and mechanism models.

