### 2.2.2 Secondary Outcomes:

- Emotional wellbeing: the Warwick-Edinburgh Mental Wellbeing Scale (WEMWBS) assesses participant's mental wellbeing and consists of 14 items, scored on a 5-point Likert scale score, giving an overall score [12].
- Anxiety and Depression: Patient Health Questionnaire 9-item (PHQ9) measures severity of depression and response to treatment. General Anxiety Disorder 7-item (GAD7) assesses the likelihood of the presence of the four most common clinical anxiety disorders [13, 14].
- Health-related quality of life:
  - FACIT F incorporates the 27 item FACT-G (Functional Assessment of Cancer Therapy – General) and measures four domains of health-related quality of life: physical, social, emotional and functional well-being.
  - EQ-5D-5L measures health status in 5 dimensions plus a visual analogue scale of self-rated health status [15].
- Physical function:
  - Performance Status: the Karnofsky Performance Scale Index allows patients to be classified as to their functional impairment, used in (p)rehabilitation [16].
  - The 6-minute walk test [17].
  - Hand grip strength [18].
- Incidence of sarcopenia: SARC-F [19]; calf circumference [20].
- Incidence of malnutrition: Utilising Malnutrition Universal Screening Tool (MUST) [21] and its determinants; % weight change, Body Mass Index (BMI), energy and protein intake (food diaries via myfood24) [22].
- Completion of consolidation treatment plan (chemotherapy +/- HSCT)
- Number of onward referrals to local services for 'specialist' therapies.
- Overall and relapse-free survival.
- Readmissions to hospital, ICU admission, number of transfusions, complications of HSCT, adverse events and serious adverse events.
- Costs, cost-effectiveness and utility: costs, health resource use and EQ-5D-5L.
- Process Evaluation: fidelity to intervention delivery and dose of intervention received for each component.
- Mechanisms of Action:
  - Psychological flexibility – is the mechanism of action for ACT, and the model within which all intervention methods are delivered. This will be measured with a shortened version (8-items) of the CompACT questionnaires [23]
  - Motivation – measured using 1-item from the COMB-Q adapted for each component (3-items total) [24].

All questionnaires being used for the patient reported outcomes have been previously validated or have been adapted from validated questionnaires to fit this specific context and patient group.

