#### **4.4.1 Method of Implementing the Trial Arm Allocation**

Participants will be randomised on a 1:1 basis to best practice usual care (BPUC) or a personalised prehabilitation care package (PPCP). Trial arms will be allocated randomly using a computer minimisation algorithm held centrally at the Warwick Clinical Trials Unit and stratified by the following variables:

- age (<= 60; >60 years)
- baseline fatigue (none, mild, moderate, severe)
- performance status (Karnofsky performance status: 100-80; 70-50; 40-0) (17)
- intention to proceed to HSCT (yes; no).

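### The primary fatigue model adjusts for treatment received, and may add compliance and dose, all arising after randomisation, so its arm coefficient is not the promised intention-to-treat effect

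*Protocol*

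**What the plan says.** Section 8.2.1 states the aim of the primary analysis plainly: "The primary analysis will be a pragmatic comparison of the PPCP versus BPUC on an intention to treat basis". The reason given is to preserve randomisation and avoid bias. Compliance is assigned to a CACE sensitivity analysis.

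The next paragraph names a single model for fatigue, a longitudinal mixed effects regression "adjusted for patient-level factors including age, performance status and treatment received". It then says that individual need, "compliance and intensity of the intervention including the number and amount of each component delivered will be investigated", with their inclusion in the mixed model to be decided after that evaluation. Red cell transfusion is also to be considered as a time-dependent effect.

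Other sections fix when these variables arise and what drives them:

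- **4.4:** randomisation takes place after remission is confirmed and before the first consolidation cycle.
- **Trial Summary:** treatment varies between patients in the number of cycles and in whether HSCT is given.
- **2.2.2:** completion of the consolidation plan is a secondary outcome.
- **1.2:** prehabilitation is expected to help patients complete all cycles and reach HSCT.
- **4.8:** dose is built from the share of prescribed sessions attended and from component tools. Patients' ability to do the activities is expected to vary with how well they feel.
- **4.4.1:** intended HSCT is a minimisation factor. The survival models in 8.2.1 adjust for the stratification factors, but the fatigue model does not name this one.

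**The concern.** Three features of the text pull against the intention-to-treat statement.

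1. **Treatment received lies on the causal path.** If PPCP helps patients complete cycles or reach HSCT, conditioning on that treatment removes part of the effect. Health during treatment drives both completion and fatigue. Conditioning on completion can therefore distort the arm comparison even if completion has no effect on fatigue.
2. **Dose has no counterpart under BPUC.** The control is one 30-minute appointment. With dose in the model, the arm coefficient describes PPCP in a person who received none of it. Because dose follows wellness, its slope also absorbs the difference between fitter and sicker patients.
3. **The final model would depend on the data.** Whether compliance and dose enter is to be settled by evaluating them, so the primary estimate and p-value are not fixed in advance.

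An effective intervention could be reported as null or harmful, and an ineffective one as harmful.

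**Working it through.** **Design figures (8.1).** Inputs: standardised difference 0.3, 90% power, 5% two-sided, 20% dropout, 1:1 allocation.

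- n per arm = 2 × (1.960 + 1.282)² / 0.3² = 233.5, so 234.
- 234 / 0.8 = 292.5, so 293. The exact t-test gives 235, then 294. The planned 300 per arm is reproduced within 3%.
- Evaluable per arm: 300 × 0.8 = 240, with power about 0.91.

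The sample size is sound and assumes a plain two-arm comparison. The protocol equates 0.3 with 4 points and an SD of 13, which are used below. A positive coefficient means benefit from PPCP.

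**Adjusting for treatment completed.** The protocol gives no figures for this, so these are assumptions:

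- 60% complete under BPUC.
- Completion shares a latent health factor with fatigue, worth 6 points per SD.
- Completion itself is worth 0 to 6 points.
- The total effect of allocation is 4 points.

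Least squares at one time point on 400,000 simulated records gave:

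| PPCP raises completion by | Arm coefficient without the term | With the term |
|---|---|---|
| 0 points | about 4.0 | about 4.0 |
| 5 points | about 4.0 | 3.4 to 3.6 |
| 10 points | about 4.0 | 2.7 to 3.3 |
| 20 points | about 4.0 | 1.4 to 2.6 |

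The upper figure in each range is the case where completion has no effect on fatigue, so that attenuation comes only from the shared health factor.

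The direction can reverse. In a separate simulation HSCT costs 6 points and PPCP raises its receipt by about 5 percentage points. The path through HSCT is then about -0.05 × 6 = -0.3. Using HSCT received instead of intended moved the estimate from 3.7 to 3.9.

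**Adjusting for dose.** Dose is zero in BPUC, so its slope is estimated within PPCP alone, and

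arm coefficient = ITT effect − (slope of fatigue on dose within PPCP) × (mean dose in PPCP).

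Assume mean dose 0.6 and SD 0.25, with latent health again worth 6 points per SD. If the correlation of dose with health is 0.3, the health part of the slope is 6 × 0.3 / 0.25 = 7.2. If a share s of the 4 points acts through dose, add 4s / 0.6.

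| Share through dose | Correlation | By formula | Simulated |
|---|---|---|---|
| 0 | 0 | 4.0 | 4.0 |
| 0.5 | 0 | 4 − 2 = 2.0 | 1.9 |
| 1 | 0 | 4 − 4 = 0 | 0.0 |
| 0 | 0.3 | 4 − 0.6 × 7.2 = -0.3 | -0.4 |
| 0.5 | 0.3 | 4 − 2 − 4.3 = -2.3 | -2.6 |
| 1 | 0.3 | 4 − 4 − 4.3 = -4.3 | -4.5 |
| True effect 0 | 0.3 | 0 − 4.3 = -4.3 | -4.6 |

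The small gaps arise because the simulated dose is confined to between 0 and 1.

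**Precision.** Take 240 per arm and an SD of 13.

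- Without dose: SE = 13 × √(2/240) = 1.19.
- With dose: SE = 13 × √(2/240 + 0.6² / (240 × 0.25²)) = 13 × √(0.0083 + 0.0240) = 2.34.

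Even in the harmless case with no bias, 4 / 2.34 = 1.7, which falls short of 1.96.

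**The case against.** The best counter-argument has four parts.

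- **Treatment received is undefined.** It could mean induction therapy or the planned pathway, both known before randomisation. This is possible but strained. Section 4.3 calls the baseline item the intended treatment pathway, and cycles and HSCT are what the protocol says vary between patients.
- **Dose is only a candidate.** The section promises intention to treat, sends compliance to CACE, and leaves full detail to the SAP. It is true that dose is not fixed in the model. But the text names the same mixed model as the place where dose may go. A SAP that follows the text inherits the problem, and one that corrects it departs from the protocol.
- **The large shifts belong to the optional term.** This stands. For treatment received, the one covariate already fixed, the shift is nil if PPCP does not change completion. It can be as small as 0.2 points, in either direction, and large attenuation needs a 10- to 20-point rise in completion. The most extreme dose results assume that the whole effect acts through dose, or that attendance follows wellness.
- **Patients are still analysed as randomised.** This is also true. What is lost is the meaning of the arm coefficient as the effect of allocation, and that coefficient is what will be reported.

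**Conclusion.** The concern holds. Section 8.2.1 states an intention-to-treat aim and then specifies a fatigue model that need not deliver it. One post-randomisation covariate is fixed in the model, and others may be added after inspection. The contradiction follows from the text and from the timing of randomisation, whatever the numbers.

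The size of the bias rests on the assumptions above, since the protocol gives no completion rates, attendance figures or correlations. It is modest for treatment received unless PPCP changes completion materially. It can exceed the 4-point target difference if dose enters the model and is related to health. Because this concerns the primary estimate, it must be settled before any unblinded analysis.

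**What to change.** In section 8.2.1:

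- State that the primary fatigue model contains arm, time and pre-randomisation covariates only: age, baseline fatigue, baseline performance status and intended HSCT. Performance status needs the word baseline because section 4.9 records it at later visits as well.
- Replace treatment received with the minimisation factor for intended HSCT.
- Delete the sentence that evaluates compliance, intensity and amount delivered for inclusion in the mixed model. Keep these variables in the CACE analysis already planned and in the process evaluation, with dose-outcome associations labelled exploratory.
- Move the time-dependent transfusion term to a labelled secondary analysis, since it also arises after randomisation.

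The cost is wording in the protocol and matching text in the SAP. No new data are needed and the sample size stays at 300 per arm.

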#### **3.1 Inclusion criteria**

- Age  $\geq$  16 years, treated on adult AML pathway

And either:

- Diagnosis of either AML or MDS-EB2 (MDS with  $\geq$ 10% blasts in the bone marrow)
- In complete remission at completion of induction chemotherapy (defined  $<$ 5% blasts in bone marrow)
- Intention to undertake consolidation treatment (chemotherapy +/- HSCT),

*\* Patients undergoing Venetoclax based treatment are only eligible if a HSCT is planned.*

**OR**

[figure not shown]
- Relapsed AML who have achieved a further complete remission, with an intent to deliver further intensive consolidation treatment +/- HSCT.
- Access to the internet and an email address.
- Willing to use videoconferencing to undertake the appointments and sessions.

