## **4.3 Baseline**

Primary and secondary outcome data will be collected prior to randomisation. Participant demographics, medical history and intended treatment pathway will be collected at baseline. A baseline participant questionnaire, with questions on health-related quality of life, and a 24hour dietary recall will be completed prior to randomisation.

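### The survival Cox models do not name entry route (first remission or relapsed AML in further remission) as a covariate; adding it is a minor, nearly free gain in precision

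*Protocol*

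**What the plan says.** Section 8.2.1 specifies that overall and relapse-free survival will be "compared across trial arms using Cox proportional hazards models, adjusted for the stratification factors". Section 4.4.1 says that allocation is by minimisation, "stratified by the following variables". It then lists four: age (two levels), baseline fatigue (four levels), Karnofsky performance status (three levels) and intention to proceed to HSCT (two levels).

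Section 3.1 gives two entry routes. One is AML or MDS-EB2 in complete remission after induction. The other is "Relapsed AML who have achieved a further complete remission", with further intensive consolidation intended. Both routes allow consolidation with or without HSCT.

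The protocol does not name entry route as a data field, but the information should be at hand. Section 4.3 states "Participant demographics, medical history and intended treatment pathway will be collected at baseline". Section 4.4 requires eligibility to be documented before randomisation, and Section 7.1 says that the case report form captures eligibility details.

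Overall and relapse-free survival are secondary outcomes (Section 2.2.2). The sample size in Section 8.1 rests on fatigue alone, and no event target or power is given for survival.

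**The concern.** The trial combines patients in remission after induction with patients who have already relapsed and reached a further remission. One of the two survival outcomes is relapse-free survival, so prior relapse is an obvious candidate for a baseline factor linked to outcome. The allocation scheme does not balance it and the stated survival models do not include it.

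Two things follow if the factor is prognostic. First, omitting a prognostic covariate from a Cox model moves the estimated treatment hazard ratio towards 1 and lowers power. Second, a chance difference between arms in the share of relapsed patients stays in the estimate. Adjustment chosen after such a difference has been seen is open to challenge; the same adjustment named in advance is routine.

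**Working it through.** **1. The plan's own figure.** The only calculated figure is for fatigue. With a standardised difference of 0.3, two-sided 5% and 90% power:

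- n per arm = 2 × (1.960 + 1.282)² / 0.3² = 234 (rounded up)
- allowing for 20% dropout: 234 / 0.8 = 293 per arm, 586 in total

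The stated 600 is within 3% of this, and 240 evaluable per arm give a power of 0.907. The figure is sound but does not bear on survival.

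**2. Inputs for the survival check.**

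- From the protocol: 600 patients, 1:1 allocation, follow-up for relapse and death to 5 years.
- Assumed, because the documents give no value: share relapsed *p* = 5%, 10%, 20%, 30%; hazard ratio of the factor *g* = 1.5, 2, 3; true treatment hazard ratio 0.75; exponential survival with 40% alive at 5 years among controls in first remission; administrative censoring uniform between 2.5 and 5 years.

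Section 1.1 cites 20% survival at 5 years for adults treated intensively. That figure is not specific to patients in remission, so it was not used. The choice affects the levels of power below.

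**3. Power with and without the factor.** Each scenario has 1,500 simulated trials. Two Cox models were fitted to the same data, one with treatment alone and one with treatment plus entry route.

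| *p* | *g* | Mean events | HR, factor omitted | HR, factor included | Power, omitted | Power, included | Gain (points) |
|---|---|---|---|---|---|---|---|
| 5% | 1.5 | 272 | 0.745 | 0.745 | 66.6% | 67.1% | 0.5 |
| 5% | 2 | 275 | 0.750 | 0.748 | 65.7% | 66.9% | 1.2 |
| 5% | 3 | 279 | 0.754 | 0.749 | 66.0% | 66.7% | 0.7 |
| 10% | 1.5 | 276 | 0.752 | 0.751 | 66.6% | 66.9% | 0.3 |
| 10% | 2 | 282 | 0.752 | 0.748 | 64.9% | 66.8% | 1.9 |
| 10% | 3 | 290 | 0.760 | 0.750 | 63.8% | 68.1% | 4.3 |
| 20% | 1.5 | 285 | 0.750 | 0.748 | 67.2% | 68.1% | 0.9 |
| 20% | 2 | 297 | 0.756 | 0.750 | 68.5% | 70.9% | 2.4 |
| 20% | 3 | 313 | 0.767 | 0.751 | 66.3% | 71.7% | 5.4 |
| 30% | 1.5 | 293 | 0.752 | 0.749 | 66.7% | 67.9% | 1.2 |
| 30% | 2 | 311 | 0.757 | 0.749 | 67.9% | 70.3% | 2.4 |
| 30% | 3 | 335 | 0.774 | 0.751 | 63.9% | 74.6% | 10.7 |

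The Monte Carlo standard error of one power figure is about √(0.67 × 0.33 / 1500) = 0.012. The paired comparison is less noisy than that, but gains below one point should be read as close to nil.

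**4. Type I error.** With a true hazard ratio of 1, the model without the factor rejected in 5.3% of trials (*p* = 10%, *g* = 2) and 4.9% (*p* = 20%, *g* = 3). The model with the factor gave the same rates.

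**5. Chance imbalance.** The standard deviation of the difference between arms in the share relapsed is √(*p*(1−*p*) × 2/300). The 95% limit is 1.96 times that, and the approximate shift in the log hazard ratio is the limit × ln *g*.

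- *p* = 5%: 1.96 × 0.0178 = 3.5 percentage points; shift 0.014 (*g* = 1.5) to 0.038 (*g* = 3)
- *p* = 30%: 1.96 × 0.0374 = 7.3 percentage points; shift 0.030 (*g* = 1.5) to 0.081 (*g* = 3)

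For scale, the 95% half-width of the log hazard ratio is about 1.96 × 2/√events. That is 0.24 with 272 events and 0.21 with 335.

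**The case against.** The strongest reply is that this is detail for the SAP. Section 8.2.1 defers full statistical detail to that document, and adjusting for the allocation factors is standard and valid. This stands in part. A reader might infer that the survival models adjust *only* for the four factors, but the text does not say so and bars no further covariate. It does, however, name a defined set for survival, whereas the fatigue model gives its covariates as examples. An SAP written from the protocol would naturally carry the defined set forward, so the stated choice is worth improving at source.

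A reader might also infer that the survival estimates will be biased or the tests invalid. They will not. Type I error holds, and chance imbalance under random allocation is sampling variation that the confidence interval already covers. The drift towards 1 is a difference between a marginal and a conditional hazard ratio, not a fault in the test.

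Three further objections stand. No section calls entry route prognostic or gives the share relapsed, so every size above rests on assumption. The simulation compared treatment alone with treatment plus entry route, without the four planned covariates. Section 1.1 links the need for HSCT to relapse risk, so HSCT intention may already carry part of the information, and the gain over the planned model would then be smaller. It cannot be assumed to carry all of it, since both entry routes allow consolidation with or without HSCT.

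Finally, it is tempting to extend the point to the fatigue model. The documents do not support that: its covariate list is open and no gain has been calculated for it.

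**Conclusion.** The point holds as a minor efficiency improvement in two secondary analyses. It is not an error in the protocol, and no stated figure is wrong.

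On the assumptions listed, naming entry route as a covariate recovers about 0-2.5 power points when the factor's hazard ratio is 1.5-2. At a factor hazard ratio of 3 it recovers about 1-5 points with 5-20% relapsed. About 11 points arises only in the corner with 30% relapsed and a hazard ratio of 3. A chance imbalance at its 95% limit would move the log hazard ratio by about 0.01-0.08, well inside the confidence interval. If entry route is not prognostic, or HSCT intention already captures it, there is little or nothing to gain. With 600 patients, one extra binary covariate would also cost very little in that case.

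**What to change.** In Section 8.2.1, and in the SAP, add entry route (first complete remission, or relapsed AML in further remission) as a prespecified baseline covariate in the overall and relapse-free survival Cox models, alongside the four minimisation factors. Make the change before any comparison of outcomes by arm is seen by those who write the plan.

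The cost is one line of text and one binary variable. Confirm that the variable can be derived from the eligibility and medical history data, since the protocol does not name it as a field. Minimisation, data collection and sample size need no change.
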